## **Study organizations:**

University of Split School of Medicine University Hospital of Split

STUDY PROTOCOL

Study location (site): Clinic for cardiovascular diseases, University Hospital of Split (UHSplit),

Split, Croatia

Anticipated start date: Jan 2018

**Anticipated end date:** April 2019

Ethical Approval: This study protocol has been independently reviewed and separately approved

by the Ethics Committee of the University of Split School of Medicine and the Ethics Committee

of the University Hospital of Split and as such has been submitted for the registration at the

Clinical Trials registry http://ClinicalTrials.gov where it was accepted and initially released on

December 19th 2017.

**Approval number:** 2181-147-01/06/M.S.-17-2

**Participant recruitment:** 

Participation in this study will be exclusively on a volunteer basis. Every eligible participant

will receive a printed material containing information about the study and an written Informed

Consent formular in Croatian language will be obtained from every subject willing to participate

in the study. Participants will be divided in two groups: a) patients being diagnosed with

congestive heart failure (NYHA II-IV) and b) healthy volunteers (matched controls).

**Procedures:** 

Every patient that has received information about the study and agreed to sign the

written Informed Consent in Croatian language will undergo non-invasive and pain-free

procedures that will include clinical examination performed by the qualified medical doctor

and/or licensed cardiologist and obtained clinical/physical examination/medical history variables

will be recorded in the study formular.

Furthermore, antecubital venous blood sampling in each patient will be undertaken by the

staff nurse for each participant enrolled in the study. These blood samples will then be used for

the analysis of the laboratory parameters at the licensed University Hospital of Split Department

2

of Laboratory Diagnostics. Laboratory parameters of interest are further explained in the text below (please refer to "Peripheral blood sampling…" section on page 4).

- Clinical examination will include the following:
  - Recording of the medical history for each participant
  - Basic anthropometric measurements: age, sex, body mass, height, body mass index (BMI), neck/waist/hip circumference
  - **Determination of smoking status**: current smoker, ex smoker, non-smoker
  - Recording of comorbidites for each patient: diabetes mellitus, dyslipidemia, arterial
    hypertension, chronic obstructive pulmonary disease and/or asthma, peripheral
    artery disease, atrial fibrillation, valvular heart disease, coronary artery disease and
    other comorbidities of interest
  - ECG records at admission and/or during index hospitalization
  - Recording of following clinical variables for chronic heart failure patients: number of previous hospitalization due to heart failure decompensation (if the pariticipant was hospitalized), medical history of prior cardiac surgeries or coronary interventions, heart failure functional classification according to New York Heart Association (NYHA) graded from II to IV and all left-ventricular ejection fractions (ranging from reduced to preserved), time of heart failure diagnosis (less than 18 months or not), medical history of acute coronary syndrome (unstable angina, NSTEMI, STEMI), medical history of stroke, current medication usage (specific entries antiarryhtmics, antihypertensives, diuretics, mineralocorticoid antagonists, digoxin, anticoagulant and/or antiplatelet therapy, special drugs such as sacubitril/valsartan or antianginals such as ivabradine, ranolazine, trimetazidine, etc.)
  - Calculation of relevant risk stratification scores for HF patients enrolled in the study such as MAGGIC risk score, Seattle Heart Failure Model (SHFM), GWTG HF, Seattle Proportional Risk Model (SPRM) and similar IN ADDITION to CHA2DS2-VASc and HASBLED scores for the subset of HF patients with a concomitant atrial fibrillation (AF)

- Transthoracic echocardiographic (TTE) examination performed by licensed cardiologistultrasonographer that will examine following variables in every participant:
  - Left-ventricular ejection fraction (LVEF, %)
  - End-diastolic dimensions of left ventricle (LVEDd, mm)
  - End-diastolic volume of left ventricle (EDV, mL)
  - End-systolic volume of left ventricle (ESV, mL)
  - Ratio of peak flow velocity in early diastole and late diastole (E/A ratio)
  - Left-ventricular mass and left-ventricular mass index (LVMI)
  - Parameters that will be recorded in selected patients for the subset analysis
    - Global longitudinal strain (GLS)
    - Right-ventricular free wall strain (RVFW strain)
    - Right-ventricular systolic function
    - Other TTE parameters of interest
- Peripheral blood sampling from the antecubital vein maximum of 22 mL will be obtained from each individual participant from both groups and following laboratory variables will be analyzed from blood samples:
  - Catestatin serum levels
  - Complete blood count, differential blood count
  - Coagulation panel (PT, APTT)
  - NT-proBNP
  - Cardiac hs-Troponin-I (hs-cTnI)
  - C-reactive Protein (CRP)
  - Creatinine, Urea, BUN
  - Electrolytes Sodium, Potassium, Calcium, Magnesium
  - Lipid profile total cholesterol, LDL-c, HDL-c, triglycerides
  - Other biochemical/blood parameters of interest

# Prospective case-controlled study - CATSTAT-HF Conducted at the University Hospital of Split **Exclusion criteria** Pool of available participants for **Inclusion criteria** the study Non-probabilistic sampling Study inclusion/exclusion Total N of participants = 120 Prospective consecutive enrollment in 3:1 fashion (HF patients: healthy volunteers) Study start: Jan 2018 90 patients with documented heart failure Healthy volunteers (matched controls) (Total left ventricular ejection fraction spectrum Total N= 30 including LVEF <40%, 40-49%, ≥50 %) Measurements 1. Basic anthropometric parameters 1. Making of individual electronic and paper record for each 2. Clinical parameters of each enrolled participant participant (medical history and physical examination) 2. Noting the loss to follow-up 3. Transthoracic echocardiography 3. Noting the attrition rate and basic hemodynamic parameters 4. Peripheral blood drawing and respective laboratory analysis Study end: Jan 2019 Statistical and data analysis

**RESULTS**

CATSTAT-HF

Official Title of the study:

Serum Catestatin Expression and Cardiometabolic Parameters in Patients With

Congestive Heart Failure (CATSTAT-HF)

NCT number:

NCT03389386

Date of the document:

April 15th 2019

Study organizations:

University of Split School of Medicine University Hospital of Split

STUDY ANALYSIS PLAN (SAP)

All data analyses will be performed by using IBM SPSS Statistics for Windows, version 23.0 (IBM Corp., Armonk, NY, USA) and/or Graphpad Prism 7 for Windows (GraphPad Software, Inc., La Jolla, CA, USA). All p-values in this study will be 2-tailed and results that reach p<0.05 will be considered statistically significant.

GENERAL STATISTICAL ANALYSES:

- 1. Descriptive analyses will provide data on particular categories of interest by using frequencies and percentages. Baseline sociodemographic, anthropometric and comorbidity burden data will be provided for each particular category.
- 2. A standard **Pearson's chi-squared test** will be used to determine statistical differences in categorical variables between the two groups of interest congestive heart failure-CHF patients vs. healthy volunteer controls and other potential subgroups of interest.
- 3. The unpaired **t-test** or **Mann-Whitney U-test**, based on the data distribution normality, will be used to determine statistical differences in continuous parameters between the two groups of interest *CHF patients vs. healthy volunteer controls* and other potential subgroups of interest, as needed. Continuous variables will be expressed as mean ± standard deviation (SD) or median ± interquartile range (IQR), based on the normality distribution.
- 4. **Bivariate Pearson correlation test (r)** is a parametric test that will be used to determine the significance of linear correlation between two continuous variables of interest (X, Y). In the determination of statistical correlation between continuous variables, a **multiple linear regression**, adjusted for confounders, will be used.

SPECIFIC STATISTICAL ANALYSES:

1. The analysis of variance (ANOVA) with post-hoc Tukey HSD test will be used to

determine statistical differences in continuous parameters among the three or more

subgroups of patients with CHF.

2. Receiver operating characteristics (ROC) curve analysis will be used to ascertain the

diagnostic sensitivity and specificity as well as corresponding cut-off values of serum

catestatin in determining heart failure (HF) degree and severity, e.g. rule out, rule in.

3. All multivariable regression analyses will be, at minimum, adjusted for age, sex, estimated

glomerular filtration rate (eGFR), and body mass index (BMI). Other important factors such as

medication intake and other potential confounding factors will be used in determining odds

ratios (OR) for the disease status (congestive heart failure). Adjusted ORs, statistical

significance (p) and 95% confidence intervals (95% CI) will be provided for independent

predictors.

Study statistical plan is provided and revised on

April 15th 2019 by

[name], BSc

[contact]

12-

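### The controls are called matched, but SAP General items 2 and 3 compare them with the heart failure patients by unadjusted tests; the main catestatin comparison should adjust for the matching factors

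*SAP*

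**What the plan says.** The Participant recruitment section of the protocol describes the comparison group as "healthy volunteers (matched controls"), and the study flow chart repeats this: "Healthy volunteers (matched controls"). The flow chart's account of how people enter the study is "Non-probabilistic sampling Study inclusion/exclusion Total N of participants = 120 Prospective consecutive enrollment in 3:1 fashion", with 90 heart failure patients and 30 volunteers. In the text available, neither document names a matching factor or a tolerance, or says whether matching is individual or by frequency.

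The SAP compares the two groups under General statistical analyses. In item 2, Pearson's chi-squared test "will be used to determine statistical differences in categorical variables between the two groups of interest". Item 3 reads: "The unpaired t-test or Mann-Whitney U-test, based on the data distribution normality, will be used to determine statistical differences in continuous parameters". Neither item has a covariate, stratum or matched-set term.

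Adjustment appears elsewhere. General item 4 plans multiple linear regression adjusted for confounders, for relations between continuous variables. Specific item 3 states: "All multivariable regression analyses will be, at minimum, adjusted for age, sex, estimated" glomerular filtration rate and BMI. It says that "medication intake and other potential confounding factors will be used in determining odds" "ratios (OR) for the disease status (congestive heart failure"). It does not say that catestatin enters this model, that its covariates are the matching factors, or that it outranks General items 2 and 3. Neither document names a primary analysis.

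**The concern.** Matching makes the groups alike on chosen factors. If those factors also predict the outcome, the analysis should account for them. A test that ignores them has an error whose direction depends on the balance achieved:

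- **Close balance in the sample.** The standard error still counts variation that the matching has removed from the difference. The test is conservative and loses power.
- **Balance in expectation only.** Type I error is about right, but power is lower than an adjusted analysis would give.
- **Systematic imbalance remaining.** The difference is biased and type I error exceeds 5%.

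If the factors do not predict the outcome, none of these applies. Consecutive, non-probabilistic enrolment does not establish which case holds. At stake is the patient-versus-control contrast in catestatin: a reader given only an unadjusted p-value could not say from the plan which way it is likely to err.

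**Working it through.** **The plan's own figures.** 30 × (1 + 3) = 120 and 90/30 = 3, so the sample size and ratio agree. The documents give no effect size, SD or power, so 120 cannot be derived from a formula and no stated figure is in dispute.

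**Inputs.** From the documents: 90 v 30, two-sided 5%. Assumed, because the documents give nothing: outcome SD 1; a true difference of 0.5 SD where power is shown; matching factors explaining R² = 10/20/30% of outcome variance; a 0.3 SD imbalance where one is shown.

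SE of the unadjusted difference = √(1/90 + 1/30) = 0.211. So 0.5 SD gives 0.5/0.211 = 2.37 standard errors.

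**1. Exact balance.** The t statistic has variance about 1 − R² instead of 1.

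- Unadjusted type I error ≈ 2[1 − Φ(1.96/√(1 − R²))] = 3.9/2.8/1.9%. Simulation of the pooled t-test gave 3.9/2.8/2.0%, and of Mann-Whitney 3.9/2.9/1.9%.
- Unadjusted power ≈ Φ((2.37 − 1.96)/√(1 − R²)) = 67/68/69%; simulated, 66/67/68%.
- Adjusted power ≈ Φ(2.37/√(1 − R²) − 1.96) = 70/75/81% with an ordinary SE. With a robust (HC3) variance, simulations gave 67–69/72–74/78–79%; 68/74/79% is used below.

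**2. Balance in expectation only.** The statistic has variance about 1. Simulated unadjusted type I error is 5.2/5.1/4.8%. Unadjusted power stays at about 65% whatever R² is (noncentral t: 65.3%), while adjusted power rises much as in case 1.

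**3. Systematic imbalance, no true difference.** A 0.3 SD shift in the factor biases the difference by 0.3√R² = 0.09/0.13/0.16 SD, or 0.45/0.64/0.78 standard errors (δ).

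- If 0.3 SD is a shift between the populations sampled, the statistic has mean δ and variance about 1: type I error 7/10/12%.
- If 0.3 SD is the imbalance observed in the sample, the variance is 1 − R²: type I error 6/7/8%.
- Adjusted: about 5% throughout.

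| Variance explained | 0% | 10% | 20% | 30% |
|---|---|---|---|---|
| Exact balance, power at 0.5 SD: unadjusted | 65% | 66% | 67% | 68% |
| Exact balance, power at 0.5 SD: adjusted, robust variance | 63–65% | 68% | 74% | 79% |
| 0.3 SD population shift, type I error: unadjusted | 5% | 7% | 10% | 12% |
| 0.3 SD observed imbalance, type I error: unadjusted | 5% | 6% | 7% | 8% |

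**4. Chi-squared test.** The same pattern appears. With factors explaining 0/8/19/37%, simulated type I error under exact balance is 5/4/3/1%; with a 0.3 SD observed imbalance it is 5/6/7/8%. A stratified test stays near 5% in both.

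**5. Form of the t-test.** Item 3 does not say pooled or Welch. Let the HF/control SD ratio be r, with control SD 1. True variance = r²/90 + 1/30. The pooled test expects [(89r² + 29)/118] × (1/90 + 1/30).

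- r = 0.8: 0.0404/0.0324 = 1.25; type I error 2[1 − Φ(1.96/√1.25)] = 8%.
- r = 1.5: 0.0583/0.0863 = 0.68; type I error 2%.
- Welch: about 5% in both.

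**The case against.** The strongest reply is that the SAP already has this in hand. Items 2 and 3 follow baseline description under the general heading and read as routine univariate comparisons. The adjusted contrast is in Specific item 3, with age, sex, eGFR and BMI at minimum, and modelling disease status is itself a patient-versus-control comparison. General item 1 also commits to reporting baseline data, so balance on age, sex or BMI would be visible afterwards. Much of this stands: it would be wrong to infer that the SAP has no adjustment. What it leaves open is whether catestatin enters that model and which result counts as the group comparison.

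A second reply is that every size above is assumed. That is so. At 0–10% explained variance under exact balance, adjustment with a robust variance changes power by only about −3 to +3 points. A material benefit needs factors that explain about 20% or more, or a systematic shift, and the documents show neither.

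A third is that unpaired tests suit frequency matching. It is true that frequency matching needs no pairing, and a reader should not infer that paired tests are required here: no linked sets are described. Frequency matching still calls for adjustment for its factors.

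Finally, matching details may stand in text that was not available, such as the eligibility criteria. Items 2 and 3 would still not use them.

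**Conclusion.** The point holds as an analysis that should be improved. The controls are called matched, the named two-group tests ignore this, and the planned odds ratio model covers confounding only in part. The size depends on two unknowns: how strongly the factors predict the outcome, and how well the groups are balanced. Over the assumed range, the cost is about 2 to 11 points of power under exact balance, or type I error of 6–8% (0.3 SD observed) to 7–12% (0.3 SD population shift) if imbalance remains. It is nil if the factors are unrelated to the outcome.

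Two stronger readings are tempting. One is that the tests have inflated type I error: the documents do not support this, since no imbalance is shown, and under close balance the error runs the other way. The other is that adjustment would make the comparison valid outright: it removes confounding only by the factors in the model, and volunteers may differ from patients in other ways.

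**What to change.** Make the main CHF-versus-control comparison of catestatin a linear model with group as a term, adjusted for the matching factors, on a transformed scale if catestatin is skewed. This requires naming those factors. A robust variance is optional. Keep the tests of items 2 and 3 as descriptive, and specify Welch's form of the t-test because of its stability at 90 v 30.

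The cost is SAP wording and a little analysis work. If the factors are age, sex and BMI, the protocol already records them for every participant, so no new data are needed. The downside is a few degrees of freedom and, if the factors turn out to be unrelated to the outcome, up to about 3 points of power with a robust variance.

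### The SAP does not say which form of unpaired t-test applies at 90 vs 30, and uses pooled-variance ANOVA/Tukey in HF subgroups; naming Welch-type methods is a cheap improvement

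*SAP*

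**What the plan says.** **Two-group comparison (SAP, General statistical analyses, item 3).** The unpaired t-test and the Mann-Whitney U-test are the two options, and the choice is "based on the data distribution normality, will be used to determine statistical differences in continuous parameters between the two groups of interest", namely CHF patients and healthy controls. The same item extends to other subgroups as needed. The pooled and unequal-variance forms of the t-test are not distinguished.

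**Three or more groups (SAP, Specific statistical analyses, item 1).** "The analysis of variance (ANOVA) with post-hoc Tukey HSD test will be used to" compare continuous parameters among three or more "subgroups of patients with CHF". Healthy controls are not part of this analysis. The item carries no check of normality or variance and no alternative method.

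**Group sizes (Protocol, study flow chart).** The total is 120, enrolled 3:1, with "90 patients with documented heart failure" and 30 healthy volunteers. The HF group covers the whole ejection fraction range, "including LVEF <40%, 40-49%, ≥50" %. The number of patients expected in each band is not given.

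**Significance (SAP, opening paragraph).** "All p-values in this study will be 2-tailed and results that reach p<0.05 will be considered statistically significant".

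Neither document mentions equal variances, a variance test, Welch's method or Games-Howell comparisons. Neither gives an SD, an effect size or a power target.

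**The concern.** A pooled t-test estimates one common variance, weighted towards the larger group. With 90 against 30, that estimate is mostly the HF variance, while the true standard error depends heavily on the variance in the 30 controls. If the two differ, the standard error is biased, and the direction depends on which group is more variable.

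Unequal spread is a reasonable expectation for some variables. HF patients are taken from NYHA II to IV and from reduced to preserved ejection fraction, and the controls are healthy. LVEF and ventricular volumes should therefore vary more among HF patients. For catestatin this is plausible, but the documents do not establish it.

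At stake is the calibration of the unadjusted CHF-versus-control comparisons. If HF patients are more variable, the main loss is power. If controls are more variable, the loss is control of false positives. ANOVA with Tukey HSD also pools variance, so the HF subgroup comparisons face a similar question, governed by the subgroup sizes and not by the 3:1 ratio.

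**Working it through.** **Inputs from the documents.** n₁ = 90 HF, n₂ = 30 controls; two-sided 0.05. The split reproduces: 120 × 3/4 = 90 and 120 × 1/4 = 30. There is no sample-size calculation to reproduce.

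**Assumed inputs.** Normal data; SD ratio (HF/control) from 0.5 to 3; HF subgroup sizes and SDs as listed below.

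**Step 1: bias of the pooled standard error.**

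Pooled SE = √{[(89·s₁² + 29·s₂²)/118]·(1/90 + 1/30)}; true SE = √(s₁²/90 + s₂²/30).

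- HF SD 1.5, control SD 1: pooled variance (89×2.25 + 29)/118 = 1.943; pooled SE 0.294; true SE 0.2415; ratio 1.22.
- HF SD 2, control SD 1: (89×4 + 29)/118 = 3.263; pooled SE 0.381; true SE 0.279; ratio 1.37.
- HF SD 1, control SD 1.5: (89 + 29×2.25)/118 = 1.307; pooled SE 0.241; true SE 0.293; ratio 0.82.

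**Step 2: type I error at 90 vs 30** (simulation, equal means; 100,000 replicates for the t-tests, 20,000 for Mann-Whitney).

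| SD HF / SD control | Pooled SE / true SE | Pooled t | Welch t | Mann-Whitney |
|---|---|---|---|---|
| 0.5 | 0.73 | 14.9% | 4.8% | 10.3% |
| 0.67 | 0.82 | 10.7% | 5.0% | 7.7% |
| 1 | 1.00 | 5.0% | 5.0% | 4.9% |
| 1.5 | 1.22 | 1.8% | 5.1% | 3.3% |
| 2 | 1.37 | 0.8% | 5.0% | 2.2% |
| 3 | 1.53 | 0.3% | 5.1% | 1.7% |

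A separate simulation with 40,000 replicates gave 1.7%, 0.7% and 10.5% for the pooled test at ratios 1.5, 2 and 0.67, which agrees within simulation error. With 60 vs 60 the pooled test stays at 5.0% to 5.1% for ratios 0.5, 2 and 3, so the imbalance drives the effect.

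**Step 3: power at 90 vs 30.** The true difference is set at 2.8 true SEs, which gives a well-calibrated test about 79% power.

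- Ratio 1: pooled 79%, Welch 78%.
- Ratio 1.5: pooled 66%, Welch 79%.
- Ratio 2: pooled 54%, Welch 79%.

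With a fixed difference of 0.8 control SD, ratio 2 gives 57% pooled and 81% Welch.

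**Step 4: ANOVA and Tukey HSD within 90 HF patients** (type I error; all sizes and SDs assumed; Tukey-Kramer form where sizes differ).

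| Subgroup sizes | SDs | ANOVA | Tukey familywise | Welch ANOVA |
|---|---|---|---|---|
| 50/30/10 | 2/1/1 | 1.4% | 1.2% | 5.0% |
| 45/25/20 | 2/1.5/1 | 2.6% | 2.5% | 4.9% |
| 30/30/30 | 1/1.5/2 | 5.6% | 5.6% | 4.9% |
| 45/25/20 | 1/1.5/2 | 10.6% | 10.7% | 5.2% |
| 40/35/15 | 1/1.3/2 | 11.7% | 12.2% | 4.7% |
| 50/30/10 | 1/1/2 | 18.2% | 18.6% | 5.3% |

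The test is conservative when the largest subgroup is the most variable, close to nominal with equal sizes, and anti-conservative when the smallest subgroup is the most variable.

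**The case against.** **The SAP never says pooled.** Welch's test is also an unpaired t-test, so silence on the form is not a commitment to the wrong one. This stands. A reader might infer that the planned p-values will be wrong, but that needs both the pooled form and unequal SDs, and the documents state neither. What remains is an unspecified choice that matters at this allocation and could be made after the data are seen.

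**The 3:1 ratio does not bear on the ANOVA.** This stands too. The ANOVA is confined to HF subgroups, so a reader who carries the 90-versus-30 argument over to it would be mistaken. Nor does that item rely on a normality check; it has no check. Its error depends on unstated subgroup sizes and SDs, and no single scenario should be quoted as its size.

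**In the likely case the pooled test is conservative.** If HF patients are more variable, a significant result still stands and the loss is power. A reader might infer inflated false positives in the main comparison. That would need healthy controls to be the more variable group, which the design does not suggest.

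**Some variables will go to Mann-Whitney instead.** A mixed HF population may give non-normal LVEF or volumes. This limits the reach of the fix. It does not rescue the plan, because Mann-Whitney also departs from 5% at 90 vs 30: 10.3% at SD ratio 0.5 and 2.2% at ratio 2.

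**The SAP also plans adjusted regressions** (Specific item 3), with age, sex, eGFR and BMI as minimum covariates. The unadjusted tests are therefore not the only inference, but they are still planned and judged at 0.05.

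**Conclusion.** The point holds in a conditional form and is a cheap improvement. General item 3 leaves the t-test form open. If the pooled form is used at 90 vs 30 and the SDs differ, the test is materially miscalibrated: type I error about 1.8% and 0.8% at HF/control SD ratios of 1.5 and 2, with about 13 and 25 points less power than Welch's test (79 − 66 and 79 − 54), and about 10.7% if controls have 1.5 times the HF SD. Greater spread among HF patients is the more plausible direction for LVEF and volumes, so lost power is the main expected consequence.

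Specific item 1 is a separate gap. It applies a pooled-variance method with no assumption check, and the assumed scenarios give about 1.4% to 2.6% (largest subgroup most variable), about 5.6% (equal sizes), and about 11% to 18% (smallest subgroup most variable).

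All of these figures assume normal data and SD ratios, and the ANOVA figures also assume subgroup sizes, that the documents do not give. They do not show that any planned p-value will be wrong.

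**What to change.** - **General item 3:** name Welch's unequal-variance t-test as the parametric two-group test. Making it the default, without a preliminary variance test, is the simplest rule. A prespecified variance rule would also remove the ambiguity.
- **Specific item 1:** replace ANOVA with Tukey HSD by Welch's ANOVA with Games-Howell comparisons, and state what is done if the data are clearly non-normal.

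**Cost.** Short wording changes, with no new data and no change in sample size. If variances are equal, the two-group test loses about one percentage point of power (78% against 79%). The SAP allows SPSS, GraphPad Prism or both, so the sponsor should confirm that the package used offers these methods.

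**Limit.** The change does not cover the Mann-Whitney branch, which is also sensitive to unequal spread at 90 vs 30. Results from that branch should not be read as a pure comparison of location where the spreads clearly differ.

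### Catestatin cut-offs are chosen and scored in the same patients without correction, so accuracy at the cut-off is modestly optimistic on average; separately, no confidence intervals are planned for the ROC results

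*SAP*

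**What the plan says.** SAP, specific statistical analyses, item 2, lists as outputs of the ROC analysis the "diagnostic sensitivity and specificity as well as corresponding cut-off values of serum" marker. It names the marker and its purpose as "catestatin in determining heart failure (HF) degree and severity, e.g. rule out, rule in". The cut-offs are thus a product of the analysis, not an input to it. Neither document gives a pre-set cut-off, a rule for choosing one, a split sample, cross-validation, a bootstrap or a second cohort.

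The protocol flow chart shows one sample at one hospital: 90 heart failure patients and 30 matched healthy controls. The binary condition for the ROC curve is not named. The protocol records candidates: "heart failure functional classification according to New York Heart Association (NYHA) graded from II to IV" (Procedures), several risk scores (Procedures), and an enrolled spectrum "including LVEF <40%, 40-49%, ≥50" % (flow chart). None is linked to item 2.

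Confidence intervals appear once, in item 3, on multivariable regression. The adjusted odds ratios, "significance (p) and 95% confidence intervals (95% CI) will be provided for independent" predictors. Item 2 has no matching sentence.

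**The concern.** A cut-off picked from a sample is fitted partly to that sample's chance features. Sensitivity and specificity read off at that point, in the same patients, are on average better than new patients would show. Which measure is affected depends on the rule. A best-point rule such as Youden's favours both. A rule that fixes one measure at a target favours only that one. The AUC, if the direction of the marker is set in advance, is not affected.

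Precision is a second, independent matter. Missing intervals do not cause the optimism, but without them a reader cannot see how loosely a small severe class pins down an accuracy figure. What is at stake is a published catestatin threshold with rule-out or rule-in claims that look firmer than the data allow.

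**Working it through.** **Inputs from the documents.** 90 heart failure patients and 30 controls (120 split 3:1). The plan gives no expected AUC, target accuracy or precision for the ROC item, so there is no figure of its own to reproduce.

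**Assumptions.** Severe/non-severe splits of the 90 patients: 18/72, 30/60 and 45/45; also 90 patients against 30 controls. Target 90%. AUC 0.50 to 0.90. Normal marker with equal variances for the Youden results only.

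**1. Target rule (exact for any continuous marker; no AUC needed).** Let the targeted class have n members and place the cut-off at the observed value that puts k = ceil(0.9n) of them on the correct side. The accuracy shown is k/n. The true accuracy at that cut-off follows a Beta(k, n+1−k) distribution with mean k/(n+1). The mean overstatement is

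k/n − k/(n+1) = k/[n(n+1)].

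| n in targeted class | k | shown k/n | expected k/(n+1) | overstated by | chance of overstatement |
|---|---|---|---|---|---|
| 18 | 17 | 0.944 | 0.895 | 0.050 | 74% |
| 30 | 27 | 0.900 | 0.871 | 0.029 | 65% |
| 45 | 41 | 0.911 | 0.891 | 0.020 | 63% |
| 60 | 54 | 0.900 | 0.885 | 0.015 | 61% |
| 72 | 65 | 0.903 | 0.890 | 0.012 | 60% |
| 90 | 81 | 0.900 | 0.890 | 0.010 | 59% |

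For rule-out, n is the number with the condition; for rule-in, the number without it. In simulation the untargeted measure was unbiased to within 0.001. Placing the cut-off midway between neighbouring values instead moves up to 0.010 of the overstatement to the untargeted measure.

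**2. Youden rule (simulation, 6,000 to 20,000 data sets per cell).** In each data set the cut-off maximising sensitivity plus specificity was chosen, and the sum shown was compared with the true sum at that cut-off. Mean overstatement of the sum:

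| Split | AUC 0.50 | 0.65 | 0.75 | 0.90 |
|---|---|---|---|---|
| 18/72 | 0.15 | 0.14 | 0.12 | 0.10 |
| 30/60 | 0.13 | 0.11 | 0.10 | 0.08 |
| 45/45 | 0.12 | 0.10 | 0.09 | 0.07 |
| 90/30 | 0.12 | 0.11 | 0.09 | 0.07 |

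The sum was overstated in 87% to 99% of data sets for AUC 0.50 to 0.75, and in 84% to 88% at AUC 0.90. The smaller class carries more of it: at 18/72 and AUC 0.65, about 0.11 falls on sensitivity and 0.02 to 0.03 on specificity.

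**3. Control.** With a cut-off fixed beforehand (45/45, AUC 0.70) the mean error in the sum was −0.001. Selecting the cut-off in the data is therefore the cause.

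**4. Precision.** Exact (Clopper-Pearson) 95% intervals: 12/18 = 67%, interval 41% to 87%; 27/30 = 90%, interval 74% to 98%. For the AUC, the Hanley-McNeil variance is

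[A(1−A) + (n1−1)(Q1−A²) + (n0−1)(Q2−A²)]/(n1·n0), with Q1 = A/(2−A) and Q2 = 2A²/(1+A).

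At A = 0.70 and 45/45 this is (0.21 + 44×0.0485 + 44×0.0865)/2025 = 0.00304, a half-width of 1.96×0.0551 = 0.11.

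**The case against.** The best case for the plan is that its only clue to a cut-off rule is the rule-out and rule-in wording, which suggests targets. Under a target rule the bias is 0.01 to 0.03 in one measure for classes of 30 or more, small beside an interval of 74% to 98% at 27/30. The 0.05 figure needs a severe class of 18, which no document supports. The larger Youden figures rest on a rule that the SAP does not name, and they shrink as the AUC rises. A short SAP that is silent on intervals also does not rule them out.

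Most of this stands as a limit on size. It does not remove the point: the direction held under both rules and in every split examined, and leaving the rule unstated keeps the larger bias open. On intervals, the plan commits to them for one analysis and not for the other. Any AUC interval that software might print would not cover sensitivity, specificity or the cut-off.

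Two stronger readings are tempting. One is that the plan was settled after the ROC curve had been seen, because the flow chart says "Study end: Jan 2019" and the SAP is dated April 15th 2019. But the protocol's opening section anticipates an end in April 2019, and the SAP closes with "Study statistical plan is provided and revised on" that date, which may mean that an earlier version existed. The documents do not settle the order of events. The other is that the undefined severity target adds to the bias. It is a separate gap in specification: it leaves the class sizes open but does not create the optimism.

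**Conclusion.** The concern holds, with modest weight. Followed as written, item 2 reports accuracy that is optimistic on average: about 0.01 to 0.03 in the targeted measure alone under a 90% target with 30 to 90 in the class (0.05 with 18), or about 0.07 to 0.15 in sensitivity plus specificity under a Youden rule for AUC 0.50 to 0.90. The direction is secure. The size is conditional on the assumed rule, class sizes and, for Youden, the AUC and a normal marker.

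A reader might infer that both measures must be inflated, or that any one result will be. Neither follows: a target rule leaves the other measure essentially unbiased, and a single study can fall on either side. The lack of planned intervals for the ROC results is a separate and certain omission from the text. No sample size or primary analysis is stated to depend on the ROC item, and the protocol does not mention it.

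**What to change.** In item 2 of the SAP:

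- State the binary target and the cut-off rule, and disclose it if either was chosen after the ROC curve was examined.
- Correct for in-sample selection with a bootstrap that reselects the cut-off in every resample, matched to the rule. For a best-point rule use out-of-bag scoring; simple optimism subtraction left bias there (sensitivity 0.615 against a true 0.566 at 18/72, AUC 0.65; out-of-bag 0.565). For a target rule correct only the targeted measure, by optimism subtraction or by reporting k/(n+1) in place of k/n; the latter assumes the cut-off sits at an observed value of the targeted class.
- Give 95% intervals for the AUC, sensitivity, specificity and cut-off. Exact binomial intervals for sensitivity and specificity serve under a target rule. Under a best-point rule, bootstrap intervals re-centred on the out-of-bag estimate covered 83% to 98% in simulation, so label them approximate.
- Label the cut-offs exploratory until externally validated.

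The choice between a target and a best point is a trade-off for the study team: a 90% rule-out target at AUC 0.65 leaves specificity at about 23% to 27%.

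The cost is a few SAP lines and no new data. The figures will look slightly less favourable and visibly imprecise, and a short bootstrap script may be needed, possibly outside the named SPSS and Prism software. If the curve has already been seen, prior choice is no longer possible, but disclosure, correction and intervals still are.
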